#### 6.11.1 Physical examination

Comprehensive physical examination should be carried out in the screening period, including head/neck/thyroid gland, eye/ear/nose/throat, respiratory system, cardiovascular system, lymph node, abdomen, skin, muscle and musculoskeletal and nervous system. Breast, anorectum and reproductive organ examination will be carried out only if clinically indicated.

Targeted examinations can be carried out during the study (including the intensive blood collection period) according to clinical symptoms and subjects' chief complaints.

After the screening period, any clinically significant abnormal physical examinations must be recorded as AEs.

#### 6.11.2 ECOG score

ECOG scoring will be carried out according to Table 1 before or after administration.

#### 6.11.3 Vital sign and height

The time points of vital signs, including blood pressure, heart rate, respiration and body temperature, will be as specified in Table 1. Patients were to rest in a seated or recumbent position for at least 5 minutes before starting the examination.

Height is measured at the screening visit only.

#### 6.11.4 Electrocardiogram

12-lead ECG examination will be performed according to Table 1-2 Schedule or at the time when any cardiac-related adverse event occurs during the study.

ECG examination should follow the following regulations:

- 12-lead ECG must be performed at least 15 minutes after the patient has a rest (in a supine or semi-recumbent position).
- ECG examination should be carried out before administration.

All ECG assessment items include:

- Heart rate
- PR interval
- QT interval: QTcB (Bazett's corrected QT interval  $[QTcB = QT/(60/heart rate)^{0.50}]$ and QTcF(QTcF = QT (60/heart rate)^{1/3})
- QRS wave group
- RR interval

## 6.11.5 Echocardiogram

All echocardiograms will be performed at time points outlined in Table 1 Schedule of Study Visits and may be used as a screening examination as long as the patient's echocardiogram is within 21 days prior to the first dose and is in compliance with protocol requirements. Left ventricular ejection fraction should be recorded in the original medical record and the eCRF.

## 6.11.6 Dermatologic examination

Dermatologic examination should be carried out according to the study visit schedule in Table 1 or if clinically indicated. The examinations must cover the whole skin. Special attentions should be paid to squamous cell carcinoma of skin, actinic keratosis and keratoacanthoma. If the dermatological examination is performed before signing an ICF, it can be used as one performed during the Screening Period provided that the examination is performed within 21 before the first dose and as per the protocol. Any new or changed skin damages from baseline during the study (including the intensive blood collection period) should be recorded in the original record and the eCRF. Once it is suspected as squamous cell carcinoma of skin or keratoacanthoma, biopsy skin should be carried out at study site and it should be diagnosed by qualified pathologist.

## 6.11.7 Ophthalmological examination

Ophthalmological examination should be carried out according to the study visit schedule in Table 1. If clinically indicated, consultation by qualified ophthalmologist should be carried out.

Examination includes anterior structures (including cornea, anterior chamber, iris and lens) and posterior structures (including optic nerve, yellow spot, retinal blood vessels, peripheral retina and vitreous body); intraocular pressure and vision should be evaluated.

Ophthalmological examination may not be repeated during the Screening Period, provided that it has been performed within 28 days before signing an ICF on the patient who discontinued previous anti-tumor therapy, with the examination report available, and that the examination conforms to the requirement of the protocol.

## 6.11.8 Laboratory test

All laboratory test time points will be performed according to the schedule of study visits in Table 1, and the test may be added according to the clinical judgment of the investigator.

All findings must be documented in the original medical record and recorded in the eCRF.

Abnormal laboratory test results, if considered to be clinically significant by the investigator, should be recorded as AEs.

Grade of laboratory test results should be judged in accordance with NCI-CTCAE V4.03.

The laboratory test items are shown in Table 10:

Table 10 Clinical	laboratory tests
-------------------	------------------

Serum biochemistry	Hematology and Coagulation	Urine routine
Glucose	Haemoglobin	
Blood urea nitrogen or urea	• Mean corpuscular hemoglobin	
Creatinine	• Mean corpuscular hemoglobin concentration	
Na	• Mean corpuscular hemoglobin volume	Protein
K	Hematokrit	Occult blood
Ca	PLT	Specific gravity
Mg	WBC	Ketone bodies
Р	Reticulocyte	Glucose
Bilirubin total and Bilirubin direct	Differential and absolute white blood cell count:	
Alkaline phosphatase	Neutrophils	
Aspartate aminotransferase	• Basophil (BASO)	
Alanine aminotransferase	• Eosinophils	
Lactic dehydrogenase	• Lymphocyte	
Creatine phosphokinase	Monocytes	
Total protein	Blood coagulation function test	
Albumin	Activated partial thromboplastin time 	
Globulin	Prothrombin time	
Triglyceride	International normalized ratio	
Lipase		
Amylase		
Thyroid function test		
Thyrotropic hormone		
Tri-iodothyronine free		
Free thyroxine		

For patients taking anticoagulants, coagulation tests will be performed according to Table 1. During the study, the blood coagulation function must be monitored according to appropriate clinical needs in case of any change in the dosage of anticoagulants.

## 6.11.9 Pregnancy tests

1

Serum pregnancy test needs to be performed on women of childbearing age within 7 days before the first dose, which is to be followed by a urine pregnancy test on Day 1 of each cycle as well as at the end of the study treatment, for confirmation of a negative result.

Female subjects without reproductive potential don't need to receive pregnancy test, defined as postmenopausal patients (amenorrhoea  $\geq 12$  months, follicle stimulating hormone  $\geq 40$  mIU/ mL) or patients with complete ovariectomy or amputation of uterus.

## 6.11.10 Contraception

Influence of DCC-2618 on sperm, conception, pregnancy and breastfeeding is unknown.

Subjects with reproductive potential should agree to adopt effective contraceptive methods. Male subjects and female subjects of childbearing potential should use adequate contraception during the study and for 6 months after discontinuation.

## 6.11.11 AE

All AEs should be evaluated, recorded and reported in accordance with ICH-GCP. Definition of AE, collection period, standard and procedure of recording, judgment and reporting of grade will be described in detail in Chapter 7.

## 6.11.12 Safety follow-up

All patients will receive safety follow-up to collect information of AEs and drug therapies including anti-tumor therapy and other treatment operations until 30 days ( $\pm 5$  days) after the last dose.

Sample collection, labeling, processing, storage and transportation should be carried out in accordance with laboratory manual.

## 6.12.2 Blood samples and data analysis

After obtaining blood concentration of DCC-2618 and metabolite DP-5439 after single dose and multiple doses, the following PK parameters will be calculated with non-compartment model, including but not limited to  $C_{max}$ ,  $T_{max}$ , AUC and  $T_{1/2}$ , etc. If necessary, group PK analysis of pharmacokinetic data will be carried out with industrial standard software on the basis of other clinical study data. Group PK report will be drafted independently and not regarded as the appendix of this study report.

# 7 Recording, grading and reporting of adverse events and serious adverse events

## 7.1 Definition of adverse events (AEs)

An adverse event is any untoward medical occurrence in a patient or subject administered a pharmaceutical product and which does not necessarily have to have a causal relationship with this treatment. Example of AEs include, but not limited to adverse signs (including abnormal findings in laboratory test) and symptoms, conditions that have a temporal relationship with use of investigational drug, regardless of causal relationship to the investigational product. AEs include new events or previous diseases with deteriorated

severity or frequency after signing the informed consent form. Adverse events include serious adverse events (SAEs) and non-serious adverse events.

Planned hospitalization or surgery for underlying disease and potential disease progression before screening should not be reported as an AE, unless the disease deteriorates accidentally during the study (e.g., surgery performed in advance).

Diagnostic and therapeutic non-invasive and invasive procedures, such as surgery, should not be reported as an AE. However, if diseases causing the implementation of these procedures meet regulations of AE in this protocol, they should be reported as an AE; in addition, if implementation of these procedures cause adverse influence to patients, they should be reported as an AE.

The severity must be judged immediately after the occurrence of an AE to confirm whether it is a SAE.

## 7.2 Judgment of severity

The investigator should confirm and record the severity of all AEs.

Severity of AEs should be evaluated from grade 1 to 5 on the basis of Common Terminology Criteria for Adverse Events (CTCAE).

For adverse events without designated CTCAE grade, criteria recommended by CTCAE may be referred to.

Grade I (mild)	Temporary symptom, treatment not indicated, subject's daily activities not influenced. Asymptomatic or mild symptoms; clinical or diagnostic observations only;
Grade II (moderate)	Mild discomfort in subject, daily activities slightly influenced, minimal, local or noninvasive intervention indicated;
Grade III (severe)	Intolerant symptoms, daily activities significantly influenced, drug therapy or other interventions indicated
Grade 4 (Life	Life-threatening; urgent intervention indicated
Threatening)	
5 (Death)	Results in death

## 7.3 Determination of drug relationship

The investigator should evaluate the causality between adverse event and the investigational drug according to the following table:

Related	Definitely related	Adverse event is related to administration of the investigational drug, there is rational possibility between the occurrence of the event and the investigational drug, and other reasons except for the investigational drug have been excluded; and/or the event reoccurs when the investigational drug is resumed
	Probably	Adverse event is related to administration of the investigational drug, there is
	related	rational mechanism between the occurrence of the event and the investigational drug, and the event cannot be rationally explained by

		patients' clinical conditions, or there is not other obvious cause
	Possibly related	Adverse event is related to administration of the investigational drug and there is rational mechanism between the occurrence of the event and the investigational drug; however the event may be induced by other causes, such as patients' clinical conditions and features of underlying diseases.
Unrelated	Possibly unrelated	Adverse event is possibly not related to the investigational drug but possibly related to other factors. It is more rational to explain from other aspects (such as concomitant medications, concomitant diseases), or the causal relationship would be impossible in terms of temporal relation.
	Unrelated	The adverse event is related to other cause than the investigational drug (this cause should be recorded in the original medical record of the patient)

## 7.4 Measures Taken to the IMPs

The investigator must clarify measures to the investigational drug due to AE. Measures taken to the investigational drug are shown in the following table:

Category	Definition
Unchanged dosage	AE doesn't lead to dose adjustment
Dose reduction	AE leads to dose reduction
Treatment discontinuation	AE leads to dose interruption
Permanent discontinuation of drug	AE results in permanent discontinuation of drug
Not applicable	
 
Select "not applicable" in case of any of the following conditions:
 
AE occurs before the administration of the investigational drug;
 
The subject died suddenly during treatment, so it is unable to take measures to investigational drug for this event;
 
The investigational drug has been discontinued before the occurrence of the AE;
 
The subject didn't take the drug when the AE occurs and the occurrence of the AE will not influence subsequent medication plan.
 

## 7.5 Outcome of adverse event

The investigator must follow all AEs until the final outcome. Outcome of AE can be recorded according to the following table:

Category	Definition
Recovered	AE recovered, without sequela
Recovered, with	AE recovered, with sequela
sequela	Select "not recovering/not resolving/persistent" for irreversible congenital
	anomaly.
	For other irreversible diseases, select "recovered, with sequela".
Recovering/resolving	AE resolving and recovering
Not recovering/not	AE not recovering, persistent
resolving/persistent	

Category	Definition
Death	Outcome of AE is death. Only when the death is possibly related to AE, can "Death" be used
Unknown	Outcome of AE is unknown, such as subject lost to follow-up

The investigator is required to continue to follow up any adverse event that has not recovered at the last visit of the study until the event is recovered or stable or resolved to baseline level or stable state of chronic diseases or it is unable to obtain more information (e.g., refusing to be followed up or lost to follow-up). Subsequent follow-up visits may not be entered into the eCRF, but the sponsor considers that there is a right to request further information from the investigator if necessary.

#### 7.6 Treatment measures taken for AEs

The investigator should ensure appropriate medical care for any AEs. In addition, the investigator should record whether treatment measures have been taken for AE. If treatment measures have been given, such as other drugs, hospitalization, surgery or physiotherapy, "yes" should be recorded; if the above treatment is not given, "no" should be recorded.

#### 7.7 Other considerations for AE

Evaluation of clinical significance

Laboratory test, ECG, physical examination and vital signs will be evaluated during the study and clinically significant abnormalities should be recorded as AEs. If possible, disease diagnosis should be first used as the name of adverse events (e.g., urinary tract infection and anemia). If the diagnosis is unable to be confirmed, abnormal test findings will be reported as AE (e.g., bacterial in urine or haemoglobin decreased). If the diagnosis is confirmed later, the diagnosis should be additionally recorded as an adverse event. If subjects meet one or several of the following conditions, abnormal study assessment will be regarded as clinically significant:

- Persistent deterioration from baseline, accompanied with corresponding symptoms or signs.
- Further diagnostic tests or drug/surgical therapies required.
- Leading to change in dose of the investigational drug, such as drug discontinuation or treatment termination.

The above criteria are not applicable to retesting to ensure whether test value is abnormal. Whether the study assessment is clinically significant should be judged by the investigator.

Grade 4 laboratory test indicator may be not a SAE, unless the patient's clinical status shows it is a life-threatening AE.

Symptoms of the studied disease should not be taken as AEs as long as these symptoms are progressive or expected progressive disease, including obvious deterioration, unless

deterioration is not caused by progressive disease and is part of the efficacy data the study will collect.

#### 7.8 Defination of SAEs

An SAE is a serious adverse event that occurs during the course of a clinical trial and may include:

- Events leading to death;
- A life-threatening event (defined as an event in which the subject was at risk of death at the time of the event, not an event that hypothetically might have caused death if it were more severe);
- Events requiring hospitalization or prolongation of hospitalization;
- An event that results in permanent or significant disability/ incapacity/ impairment of work;
- Results in congenital abnormality or birth defect;
- Other important medical events, defined as an event that may not lead to death, be life-threatening, lead to hospitalization, but may jeopardize the subject or may require medical intervention to prevent one of above listed outcomes (e.g., allergic bronchospasm, aggressive treatment at emergency or home required, cachexia or convulsion, or drug dependence or drug abuse).

The following were not to be reported as SAEs:

- Any outcome, including death, due to progression of the patient's primary tumor disease as assessed by the investigator.
- Hospitalization or prolonged hospitalization due to economic issue or for purpose of reimbursement only.
- Elective surgery scheduled prior to the start of study treatment.
- Prescription or study-related examinations can be carried out only during hospitalization for hospital management reasons

## 7.9 Adverse Events of Special Interest (AESIs)

The following adverse events occurring after starting of the investigational drugs require special interest:

- Squamous cell carcinoma of skin
- Actinic keratosis
- Keratoacanthoma

Patients with squamous cell carcinoma of skin, actinic keratosis and/or keratoacanthoma

should be managed according to dermatologist and local guidance.

For the above adverse events of special interest, it is required to fill in the "AESIs Report Form" within 24 hours upon the investigator's awareness, and report to the sponsor via email: **[contact]**. If the event meets the criteria for an SAE, it is required to fill in the "Clinical Study SAEs Report Form" and it will be reported directly to the sponsor according to the SAE reporting process.

## 7.10 Time Limit for Collection of Adverse Events

Collection and recording of adverse events (including SAE and AESI) will be carried out throughout the study, from the date of signing the informed consent form (ICF) to 30 days after the last dose of the investigational drug; if the patient starts new anti-tumor therapy, the deadline for collection of AEs will be the date of starting new anti-tumor therapy; any SAEs or AESIs occurring after the time limit for collection of AEs should be reported immediately if suspected to be possibly related to the investigational drug.

## 7.11 Requirements for reporting AE, SAE and AESI

Whether AE occurs should be monitored seriously in each subject. Information of AEs can be obtained by non-induced questions to subjects (e.g., how do you feel?), signs and symptoms of clinical examination, observation of subjects and chief complaints of subjects. Information of AEs obtained by the above methods should be recorded in the original medical record and the eCRF.

If possible, disease diagnosis should be first used as the name of adverse events. If a unifying diagnosis is not available, then associated symptoms and signs are to be captured. Once the diagnosis is confirmed with the follow up information, the symptoms and sign should be replaced with diagnosis accordingly.

Any SAE occurring during the reporting period, whether or not related to the investigational drug, should follow the SAE reporting procedures of the relevant regulatory authorities or the Independent Ethics Committee.

The investigator should:

- (1) If necessary, take appropriate medical measures immediately to ensure the safety of patients;
- (2) Record SAEs in the AE Form, SAE Form and source documents of eCRF.
- (3) The investigator should immediately fill in the "Clinical Study SAEs Report Form", sign the name and date, and report it to the sponsor within 24 hours upon awareness of the event (public email mailbox of Drug Safety Department in Zai Lab: [contact]).
- (4) The course of the event was to be followed up and documented until recovery or
return to baseline values or until a clinically stable status was reached or the investigator agreed with the sponsor that no further follow-up was necessary. For the purpose of study analysis, events that are not recovered during the study report period should be recorded as persistent.

DCC-2618 may be continued until disease progression, death, or intolerable toxicity, or patient's request to discontinue treatment, in the opinion of the investigator, for patients who remain on investigational drug after the clinical trial database has been closed, if clinical benefit is sustained, Such patients will only be monitored for all serious adverse events until 30 days after the last dose of investigational product. The investigator should still collect information of drug management and accountability until all patients have finished the treatment.

• Treatment of Death Cases

All deaths occurring during the study, including within 30 days after the last dose of investigational drug, during the safety follow-up period of the last dose of investigational drug will be reported by the investigator as follows:

- If death is caused by disease progression, the investigator should notify the Sponsor's monitor of the event in the next site monitoring visit and record it in relevant section of eCRF, but it will not be reported as a SAE.
- If it is not determined whether the death is caused by disease progression, the AE should be reported as a SAE, informed to the monitor and reported to the relevant parties within 24 hours; the SAE report should evaluate whether the disease progression jointly contributed to the death of the subject and indicate the main cause of death and other related factors, as appropriate.
- Death cases with unknown causes must be reported within a specified time-line in accordance with the SAE, and the cause of death should be clarified with every effort. Autopsy may be conductive to assessment on the cause of death. If an autopsy is performed, the Sponsor should be notified of the autopsy report.
- Reporting and follow-up of AESI

AESI occurring in the reporting period should be reported to the sponsor within 24 hours of awareness. Follow-up on AESI will be pursued until they are recovered/resolved to the baseline level or clinically stable or the investigator and the sponsor consistently consider follow-up is not required. For the purpose of study analysis, events that are not recovered during the study report period should be recorded as persistent.

• Suspected unexpected serious adverse reaction (SUSAR)

If SUSAR related to the investigational drug occurs, the sponsor should expeditedly report to relevant regulatory authorities and all investigators and clinical trial institutions and ethics

committee taking part in the clinical trial. After receiving the relevant safety information of the clinical trial provided by the sponsor, the investigator should sign and read it in time, and consider whether to make corresponding adjustments to the treatment of the subject. If necessary, the investigator should communicate with the subject as soon as possible, and should report to the ethics committee SUSAR provided by the sponsor.

• Pregnancy

Effective contraception is required for both male and female subjects of childbearing potential during the trial and for 6 days after discontinuation of investigational drug. If a subject is found to be pregnant following initiation of study treat, the investigational drug will be permanently discontinued and the subject will be withdrawn from the trial. If a partner of a male subject becomes pregnant during the study or within 6 months after the last dose of investigational drug, the investigator should be informed immediately. The investigator must fill in the "Clinical Study Pregnancy Exposure Reporting Form" and expeditedly report to the via email upon 24 hours of becoming aware of sponsor pregnancy ([contact]). At the same time, the pregnancy also must be recorded on eCRF. All pregnancies must be followed to conclusion to determine their outcome. If the outcome of the pregnancy meets SAE criteria (e.g., spontaneous abortion/miscarriage or therapeutic abortion with any detected congenital anomaly, stillbirth, neonatal death, or birth defect), it will be reported as SAE. The investigator should send the completed "SAE Reporting Form" to the Sponsor via email within 24 hours of becoming aware of the event. All pregnancies during the trial or within 180 days after discontinuation should be handled in accordance to the procedure described above. If necessary, the follow-up period will be prolonged to newborn.

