## **1.3.1.2** Clinical Pharmacokinetics and Pharmacodynamics

It was confirmed in non-clinical study that DP-5439 as an active metabolite had a similar activity with the original drug DCC-2618. Long half-life of metabolite (30 - 60 hours) supports the dosing regimen on a once daily basis. Food influence study showed that DCC-2618 taken with food did not have influence on absorption.

The mean  $T_{1/2}$  of DCC-2618 ranged from 8.04 - 11.1 hours and was evaluated only in the single dose group. Detected active metabolite DP-5439 was about 50 - 200% of the original drug (DCC-2618). Half-life of DP-5439 was not calculated.

Study personnel compared the rate of accumulation of DCC-2618 and DP-5439 on C1D15 and C1D1. For QD dosing regimen, in terms of  $C_{max}$  and  $AUC_{0-12}$ , the rate of accumulation of DCC-2618 was 0.725 - 1.47 and 0.707 - 1.69, respectively. In terms of  $C_{max}$  and  $AUC_{0-12}$ , the rate of accumulation of DP-5439 was 0.968 - 3.46 and 1.32 - 4.88, respectively.

From 100 mg QD to 250 mg QD, exposure of DCC-2618 and DP-5439 was likely to be proportional to the dose. Because pharmacokinetices of the drug changes rapidly and sample size for each dose level was small, formal PK linear correlation assessment was not carried
out.

For GIST patients who have received multiple prior treatments, DCC-2618 could rapidly eliminate plasma cfDNA with broad-spectrum KIT mutations. Overall, total plasma concentration ( $C_{max}$ ) in the 100 mg BID group on C1D15 was very high, more than 5  $\mu$ M (3,000 ng/mL); the observed mean exposure was far more than the target plasma level, including exposure level for KIT mutations (V654A and T670I) most insensitive to DCC-2618.

At baseline, all GIST patients received next generation plasma free DNA sequencing (cfDNA) once every 2 cycles during the study. Mutations were tested and quantified with Guardant 360 v2.9 or v2.10. Amino acid mutation only in KIT and PDGFRA was regarded as resistance-conferring mutations. Free DNA was not detected in all patients. According to the preliminary data, 19 unique gene mutations were observed in GIST patients with 11/29 KIT mutations. In exons 9. 11, 13, 14, 17 and 18, a total of 43 mutations were detected in KIT gene. Of 4 enrolled patients with PDGFRA D842V-mutation (confirmed according to previous archived results of patients), PDGFRA D842V-mutation was detected only in the sample of one patient.

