## 4.2 Exclusion Criteria

Subject meeting any of the following criteria should not be enrolled in this study:

- 1. Treatment with anticancer therapy, including investigational therapy, or investigational procedures within 14 days or 5 x the half-life (whichever is longer) prior to the first dose of investigational drug. For prior biological therapies, eg, monoclonal antibodies with a half-life longer than 3 days, the interval must be at least 28 days prior to the first dose of investigational drug.
- 2. Prior treatment with DCC-2618.

- 3. Previously or currently has an additional malignancy that is progressing or required active treatment, which may interfere with the safety or efficacy evaluation of DCC-2618. If the patient is receiving the adjuvant therapy that is likely to be effective for GIST or should be excluded based on the protocol (see Section 5.9.3), the patient should not be included in this study.
- 4. Patient has known active central nervous system metastases.
- 5. New York Heart Association class II IV heart disease, active ischemia or any other uncontrolled cardiac condition such as angina pectoris, clinically significant cardiac arrhythmia requiring therapy, uncontrolled hypertension or congestive heart failure.
- 6. Arterial thrombotic or embolic events such as cerebrovascular accident (including ischemic attacks) or hemoptysis within 6 months before the first dose of investigational drug.
- Venous thrombotic events (eg, deep vein thrombosis) or pulmonary arterial events (eg, pulmonary embolism) within 3 months before the first dose of investigational drug. Patients with venous thrombotic events ≥3 months before the first dose of investigational drug on conventional anticoagulation therapy are eligible.
- 12-lead electrocardiogram (ECG) demonstrating QT interval corrected by Fridericia's formula >450 ms in males or >470 ms in females at screening or history of long QT interval syndrome.
- 9. Left ventricular ejection fraction (LVEF) <50% at screening.
- 10. Use of strong or moderate inhibitors and/or inducers of cytochrome P450 (CYP) 3A4, including certain herbal medications (eg, St. John's Wort) and consumption of grapefruit or grapefruit juice within 14 days or 5 x the half-life (whichever is longer) prior to the first dose of investigational drug.

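### Section 7.11 requires contraception for 6 days after stopping the drug where section 6.11.10 requires 6 months; 6 days is almost certainly a unit slip

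*Combined protocol and SAP*

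**What the plan says.** Four statements in the protocol set a period after treatment that concerns pregnancy.

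- Section 7.11, Pregnancy: effective contraception for male and female subjects of childbearing potential during the trial and "for 6 days after discontinuation of investigational drug".
- Section 6.11.10, Contraception: male subjects and female subjects of childbearing potential "should use adequate contraception during the study and for 6 months after discontinuation".
- Section 7.11, same paragraph: the investigator must be told if a male subject's partner becomes pregnant during the study or "within 6 months after the last dose of investigational drug".
- Section 7.11, same paragraph: "All pregnancies during the trial or within 180 days after discontinuation should be handled" by the procedure given there.

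Inclusion criterion 6 (section 4.1) makes agreement to the contraception rules a condition of entry, but gives neither a duration nor a section number. Section 6.11.10 also states the reason for caution: "Influence of DCC-2618 on sperm, conception, pregnancy and breastfeeding is unknown".

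**The concern.** Two operative sections give different durations for one obligation, and neither refers to the other or says which prevails. Site staff who look under the Pregnancy heading in 7.11 find 6 days. The instruction protects participants, their partners and any fetus, and the drug's effects on reproduction are not known.

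Later study procedures would not reliably reveal the error. Under section 6.11.9 and Table 1 the last scheduled pregnancy test is at the end-of-treatment visit, within 7 days after the last dose. The monthly survival calls (sections 6.4 and 6.10.2) ask about survival and anti-tumor therapy, not about contraception or pregnancy.

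**Working it through.** **Comparison of the text.** The protocol has no calculation to reproduce here, so the check is whether the statements can be reconciled.

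| Section | What it governs | Counted from | Period |
|---|---|---|---|
| 7.11 | Contraception | Discontinuation | 6 days |
| 6.11.10 | Contraception | Discontinuation | 6 months |
| 7.11 | Notification of partner pregnancy | Last dose | 6 months |
| 7.11 | Handling of pregnancies | Discontinuation | 180 days |

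The first two rows cover the same people from the same event, so they cannot be read as separate rules. The other two rows are reporting windows, not contraception periods. They agree with 6.11.10, since 180 days / 30 = 6 months, and they stand in the same paragraph as the 6 days. The number 6 is common to three of the four rows and only the unit differs, which is what a unit slip looks like.

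**Size of the discrepancy.** Taking 6 months as the 180 days used in 7.11:

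- 180 − 6 = 174 days shorter
- 180 / 6 = 30-fold

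This is a shortfall in required contraception, not 174 days of drug exposure.

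**Could 6 days be a deliberate washout period?** This is a plausibility check only. Inputs:

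- DP-5439, the active metabolite: section 1.3.1.2 says "Long half-life of metabolite (30 - 60 hours) supports the dosing regimen". The same section also says "Half-life of DP-5439 was not calculated", so the range is uncertain.
- Parent drug: mean half-life 8.04 to 11.1 h, same section.
- Yardstick: five half-lives with first-order elimination, an assumption. The protocol uses a related rule for washout of other drugs, "within 14 days or 5 x the half-life (whichever is longer) prior to the first dose of investigational drug" (section 4.2).

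Five half-lives in days = 5 × half-life in hours / 24. Fraction left after 6 days (144 h) = 0.5^(144 / half-life).

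| | Half-life | Five half-lives | Half-lives in 144 h | Left at day 6 |
|---|---|---|---|---|
| DP-5439, low | 30 h | 5 × 30 / 24 = 6.25 days | 144 / 30 = 4.8 | 0.5^4.8 = 3.6% |
| DP-5439, high | 60 h | 5 × 60 / 24 = 12.5 days | 144 / 60 = 2.4 | 0.5^2.4 = 18.9% |
| Parent, low | 8.04 h | 5 × 8.04 / 24 = 1.7 days | – | – |
| Parent, high | 11.1 h | 5 × 11.1 / 24 = 2.3 days | – | – |

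Six days covers five half-lives of the parent drug but not of the metabolite, at either end of the stated range. It is therefore hard to defend as an intended value.

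**The case against.** The strongest reply is that this is an editorial erratum. The rule is stated correctly in the section named for it, which is the natural reading of inclusion criterion 6, and the reporting windows in 7.11 work as intended despite the slip. That is fair, and it is why the point ranks no higher than a correction that should be made. It does not justify leaving the wrong period in a protective instruction.

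Further objections, and what stands of each:

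- **Only two of the four periods are contraception periods, and those two disagree.** Correct. The reporting windows are evidence of what was intended, not competing statements of the rule.
- **The half-life argument is soft.** Also correct. The input is uncertain, the section 4.2 rule concerns prior medication and has a 14-day minimum, and at 30 h the gap is only 6.25 − 6 = 0.25 days, or six hours. No document gives a concentration below which conception is safe, so the residual percentages do not measure risk. The contradiction stands without them.
- **The absence of a pregnancy test after the end-of-treatment visit is a separate matter.** It would be so whatever 7.11 said. It bears here only because no later test would expose the mistake.
- **Few patients may be affected.** Section 1.2 places GIST mostly at ages 55 to 65, so women of childbearing potential may be few among about 35 subjects. The rule also covers men, entry is open to any adult, and the number of reproductive potential is not stated.
- **The slip may exist only in the English text.** This cannot be excluded. The document shows signs of translation, and the consent form was not available for review. That no site or patient was misinformed is possible; that the text conflicts is certain.

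**Conclusion.** The concern holds: section 7.11 is wrong as written. The conflict between 6 days and 6 months is direct, lies in current text and is not resolved elsewhere in the protocol. That 6 months was intended is an inference, but a strong one. The literal shortfall is 174 days, on the assumption that 6 months means the 180 days used in 7.11. The comparison with metabolite half-lives rests on an uncertain range and a conventional yardstick, and the conclusion does not depend on it. Whether any participant received the wrong instruction is unknown. There is no effect on the design, sample size, power or primary analysis.

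**What to change.** 1. In the Pregnancy paragraph of 7.11, replace 6 days with 6 months (180 days).
2. Use that same period and unit in 6.11.10 and in the two reporting windows in 7.11.
3. Add a cross-reference to section 6.11.10 in inclusion criterion 6.
4. Confirm that the consent form and the protocol version used at sites give 6 months, and notify sites if theirs carries the error.

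The essential change is one word. The rest is a cross-reference, consistent units and a document check, with a site notification only if needed. The statistical analysis does not change.
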